- 8. Validation Requirements.....39
- 9. References39

1. Version History

Version	Summary of Changes	Author(s)/Title
1.0	
 Initial Release 	██████████ Principal Biostatistician
2.0	
 Revision to update statistical analysis approach, defining of endpoints and other analysis, and provide guidance on methodology of data utilization. 	██████████ Biostatistician ██████████ Biostatistician

2. List of Abbreviations and Definitions of Terms

Abbreviation	Abbreviated Term	Definition
AE	Adverse Event	Any untoward medical occurrence, unintended disease or injury, or untoward clinical signs (including abnormal laboratory findings) in subjects, users or other persons, whether or not related to the investigational medical device. NOTE 1: This definition includes events related to the investigational medical device or the comparator. NOTE 2: This definition includes events related to the procedures involved. NOTE 3: For users or other persons, this definition is restricted to events related to investigational medical devices.
CEC	Clinical Events Committee	Independent committee responsible for the review and adjudication of events that are identified to be adjudicated that occur over the course of the Study.
CSR	Clinical Study Report	Clinical Study Report
DAPT	dual antiplatelet therapy	dual antiplatelet therapy
DRF	Data Release Form	Data Release Form
eCRF	Electronic Case Report Form	An electronic document designed to record all of the protocol requested information to be reported to the sponsor on each study patient. eCRFs are "living documents" in the respect that new information on the patient is continually gathered throughout the study.

Abbreviation	Abbreviated Term	Definition
FAS	Full Analysis Set	The Full Analysis Set (FAS) population is a subset of ITT including only those subjects in whom the Pipeline™ device was implanted.
FDA	Food and Drug Administration	Food and Drug Administration
IA	Intracranial aneurysm	Intracranial aneurysm
ICF	Informed Consent Form	The written, signed and dated document that provides objective evidence of the process by which a patient voluntarily confirms his or her willingness to participate in a particular study, after having been informed of all aspects of the trial that are relevant to the patient's decision to participate (21 CFR 50).
ICH	International Conference for Harmonization	An Organization whose main purpose is to achieve greater harmonization to ensure that safe, effective, and high-quality medicines are developed and registered in the most resource-efficient manner.
IDE	Investigational Device Exemption	An approved IDE permits a device that would otherwise be required to comply with a performance standard or would require a premarket approval to be shipped lawfully for the purpose of conducting investigations of that device (21 CFR 812).
I/E	Inclusion/Exclusion Criteria	A list of conditions that would include or exclude a patient from enrolling/participating in a clinical study as outlined in the study protocol.
Implant Failure	Implant Failure	Enrolled subjects who underwent the study procedure and in whom an attempt to implant the device was made but was unsuccessful

Abbreviation	Abbreviated Term	Definition
IRB	Institutional Review Board	Any board, committee, or other group formally designated by an institution to review biomedical research involving subjects and established, operated and functioning in conformance with 21 CFR 56.
ITT	Intent-to-Treat	The Intention to Treat (ITT) population includes all enrolled subjects in whom deployment of the Pipeline™ device with Shield Technology™ was attempted. It is possible that the Pipeline™ device with Shield Technology™ may not reach the target site and the operator would not attempt to deploy it, in the rare event that happens, that patient will not be considered part of the ITT population.
MedDRA	Medical Dictionary for Regulatory Activities	Standardized medical terminology developed by ICH to facilitate sharing of regulatory information internationally for medical products used by humans. It is used for registration, documentation and safety monitoring of medical products both before and after a product has been authorized for sale. Products covered by the scope of MedDRA include pharmaceuticals, vaccines and drug-device combination products.

Abbreviation	Abbreviated Term	Definition
mRS	Modified Rankin Score	Scale for measuring general neurological function. 0 No symptoms at all 1 No significant disability despite symptoms; able to carry out all usual duties and activities 2 Slight disability; unable to carry out all previous activities, but able to look after own affairs without assistance 3 Moderate disability; requiring some help, but able to walk without assistance 4 Moderately severe disability; unable to walk without assistance and unable to attend to own bodily needs without assistance 5 Severe disability; bedridden, incontinent and requiring constant nursing care and attention 6 Dead
NIHSS	National Institute of Health Stroke Scale	Method for quantifying neurologic deficits developed by the National Institutes of Health. It is used to assess the severity of a stroke.
PED	Pipeline Endovascular Device	Pipeline Endovascular Device

Abbreviation	Abbreviated Term	Definition
Primary Efficacy Endpoint	Complete aneurysm occlusion (defined as Raymond-Roy grade 1 ⁵⁵) without significant parent artery stenosis (\leq 50%) or retreatment of the target aneurysm 1-year post-procedure	The primary effectiveness endpoint assessed by: 
• Occlusion status: by a 3-member adjudicated read by the imaging Core Laboratory according to the Scale of Roy• Parent Artery stenosis: by the 3-member adjudicated read by the imaging Core Laboratory.• Retreatment: by the investigator reported events of retreatment.

Abbreviation	Abbreviated Term	Definition
Primary Safety Endpoint	Major Stroke or Neurological Death at 1 year	
Stroke Definition:
 
A focal neurological deficit of presumed vascular origin persisting more than 24 hours from symptom onset and a neuro-imaging study or other quantitative study that does not indicate a different etiology.
 
The definition includes subjects presenting with clinical signs and symptoms suggestive of subarachnoid hemorrhage, intracerebral hemorrhage, or cerebral ischemia. The definition also includes sudden loss or worsening of vision due to retinal artery occlusion or retinal emboli.
 
The definition excludes slowly progressive cranial nerve palsies or progressive visual field deficits due to continued aneurysm growth. The definition also excludes external events such as trauma and also excludes transient ischemic attacks in which the symptoms resolve on their own within 24 hours.
 
Stroke will be classified by the Clinical Events Committee as major or minor:
 
 • Major Stroke: A stroke, in which the NIHSS of the subject increases by ≥ 4 and persists for 7 days and more. 
Minor Stroke: A stroke, which resolves completely within seven days OR increases the NIHSS of the subject by ≤ 3.

Abbreviation	Abbreviated Term	Definition
SAE	Serious Adverse Event	Adverse event that a) led to death, b) led to serious deterioration in the health of the patient, that either resulted in 1) a life-threatening illness or injury, or 2) a permanent impairment of a body structure or a body function, or 3) in-patient or prolonged hospitalization, or 4) medical or surgical intervention to prevent life-threatening illness or injury or permanent impairment to a body structure or a body function, c) led to fetal distress, fetal death or a congenital abnormality or birth defect. NOTE: Planned hospitalization for a pre-existing condition, or a procedure required by the CIP, without serious deterioration in health, is not considered a serious adverse event.
SADE	Serious Adverse Device Effect	Adverse device effect that has resulted in any of the consequences characteristic of a serious adverse event.
SAP	Statistical Analysis Plan	Statistical Analysis Plan
SD	Standard Deviation	Standard Deviation
UADE	Unanticipated Adverse Device Effect	Any serious adverse effect on health or safety or any life-threatening problem or death caused by, or associated with, a device, if that effect, problem, or death was not previously identified in nature, severity or degree of incidence in the Investigational Plan or application (including a supplementary plan or application), or any other unanticipated serious problem associated with a device that relates to the rights, safety, or welfare of subjects.
ULN	Upper Limit of Normal	Upper limit within a particular range.
USADE	Unanticipated Serious Adverse Device Effect	Serious adverse device effect which by its nature, incidence, severity or outcome has not been identified in the current version of the risk analysis report.

3. Introduction

This document provides a detailed description of the statistical methods and procedures to be implemented during the analysis of the SHIELD study. The methods and procedures described in this document are intended to support the generation of a Clinical Study Report (CSR) for Clinical Protocol NV-PED-10, including detailed descriptions of the populations, methodologies, post-text tables, analysis summary tables, patient data listings, and descriptive graphics. The information collected during this clinical investigation will be used to assess specific parameters and contrast these results with other Pipeline studies where the Pipeline device did not have the Shield Technology™. Likewise, the information analyzed herein will help us to assess safety and efficacy of the device for, but not limited to, a US indication evaluation.

This study is a multi-country, prospective, single-arm, multi-center clinical investigation evaluating outcomes in subjects with intracranial aneurysms who are treated with the Pipeline™ Flex Embolization Device with Shield Technology™. Within this current study, the safety and effectiveness of the Pipeline™ Flex Embolization Device with Shield Technology™ device in subjects undergoing treatment for intracranial aneurysms will be analyzed.

Subjects will be considered enrolled in the study once the patient has signed and dated the Informed Consent or DRF and the Pipeline™ Flex Embolization Device with Shield Technology™ is advanced into the micro catheter inside the patient.

The study population will consist of patients who have an intracranial aneurysm and qualify for enrollment into the study. The treated aneurysm may be ruptured (with a Hunt and Hess grade of ≤ 3); under these clinical conditions, Pipeline™ Flex Embolization Device with Shield Technology™ may be used according to the Instructions for Use and the intended use statement during the treatment regimen. The term Primary Study Procedure refers to the initial study procedure and is used consistently to discriminate between the primary study procedure and re-treatment of the target aneurysm. If more than one aneurysm can be covered by a single Pipeline device or two overlapped devices, the multiple aneurysms treated by that device(s) may all be included in the study. If the patient has more than one aneurysm and all aneurysms requiring treatment cannot be covered by a single Pipeline device or two overlapped devices, the non-target aneurysms should be treated first. After waiting at least 30 days, the patient may return for treatment of the target aneurysm with the Pipeline™ Flex Embolization Device with Shield Technology™.

The maximum number of subjects to be enrolled in this clinical investigation is 200. The maximum number of sites permitted to participate in this clinical investigation is 25 with no more than 30 subjects enrolled per site.

All images taken of the aneurysm (e.g., angiograms, CT, MR, rotational angiography with 3D reconstruction, cone beam CT, etc.) will be sent to the Independent Core Lab designated for this clinical investigation for adjudication.

The planned analyses identified in this statistical analysis plan (SAP) may be included in regulatory submissions and/or future manuscripts. Exploratory analyses, not identified in this SAP, may be performed to support the clinical development program. Any post-hoc, or unplanned, analyses that are performed but not identified in this SAP will be clearly identified in the CSR. The structure and content

of this SAP provides sufficient detail to meet the requirements identified by the FDA and International Conference on Harmonization of Technical Requirements for Registration of Pharmaceuticals for Human Use (ICH): Guidance on Statistical Principles in Clinical Trials.

This statistical analysis plan (SAP) is based on revision B of the protocol dated 24-Jun-2016.

4. Study Objectives

The primary objective of this study is to assess the *outcomes* of the Pipeline™ Flex Embolization Device with Shield Technology™ in patients undergoing treatment for intracranial aneurysms in a large real-world, post-market setting. *Outcomes* will be assessed based on a series of standardized measurements recorded during the procedure and during the post-procedure follow-up period.

Attributes and parameters to characterize the outcomes of the Pipeline™ Flex Embolization Device with Shield Technology™ during the procedure will be addressed based on the following assessments (as observed):

- Successful deployment of the study device to the target site
- Implantation of the study device
- Entire IA neck covered by the study device
- Device malfunction during the delivery system preparation
- Adverse Events: By seriousness (Serious or Non-Serious) peri-procedural (Day 0), by relatedness (Procedure, Device and Anti-platelet therapy)

Attributes to characterize the outcomes of the study device post-procedure will be addressed based on the following assessments:

- Aneurysm occlusion (Class 1: Complete obliteration, Class 2: Residual neck, or Class 3: Residual Aneurysm)
- Adverse events: By Seriousness (serious and non-serious) ; per relatedness (procedure, device or antiplatelet therapy) and time of event (Acute 1-30 days, and Delayed 31-Study exit)
- Modified Rankin Scale (mRS)
- NIH Stroke Scale (NIHSS)
- Retreatment
- Major stroke in the territory supplied by the treated artery or neurological death
- Delayed Intracerebral hemorrhage (ICH) > 30 days post-procedure
- Parent artery stenosis (per Core Lab)
- Device migration (per Core Lab)

5. Investigation Plan

A prospective, single-arm, multi-center post-market observational study.

Up to 200 subjects who meet the Inclusion/Exclusion Criteria may be enrolled over a period of approximately 2 years to reach a target number of subjects. Study participation includes initial screening

and baseline evaluation, treatment using the Pipeline™ Flex Embolization Device with Shield Technology™, and follow-up visits at the discretion of the treating physician for 1 year beyond the index procedure. The total study duration is expected to be approximately 3 years.

Study Design:

Subjects will be considered enrolled in the study once the patient has signed and dated the Informed Consent or DRF and the Pipeline™ Flex Embolization Device with Shield Technology™ is advanced into the micro catheter inside the patient. All enrolled subjects who underwent the study procedure and in whom an attempt to implant the device was made will be included in the analysis population.

A CEC will be in place for the study using a minimum of three physicians knowledgeable in the appropriate disciplines and medical specialties pertinent to the disease state being evaluated in this clinical study. This committee will be responsible for the review and adjudication to the study variables of all events identified in the CEC Charter/Manual of Operations.

The CEC will independently adjudicate to specified endpoint event definitions, event relatedness, event severity, and event outcomes.

The imaging core laboratory will be responsible for the qualitative image analysis to determine aneurysm occlusion, parent artery stenosis, and device migration. An imaging protocol will be provided to the site.

Pre-Specified Study Endpoints:

The pre-specified study endpoints and analysis listed here are the primary body of data that will be collected, analyzed, and summarized in a series of tables, lists, and graphs as part of the final report for this study. Other analysis will be conducted as part of the final report but these are the core set of analyses that will constitute the foundation of the clinical study report.

Primary endpoints:

Safety:

- Occurrence of major stroke in the territory supplied by the treated artery or neurological death post-procedure (1-year)

Effectiveness:

- Complete aneurysm occlusion (defined as Raymond-Roy grade 1) without significant parent artery stenosis ($\leq 50\%$) or retreatment of the target aneurysm post-procedure (1-year)

Secondary endpoints:

Safety:

- Occurrence of major stroke in the territory supplied by the treated artery or neurological death at 30 days post-procedure due to procedural complications
- Delayed intracerebral hemorrhage > 30 days post-procedure

Effectiveness:

- Device deployment success rate at the target site

Additional Safety Analyses:

- [REDACTED]
- [REDACTED]

- [REDACTED]
 - [REDACTED]
 - [REDACTED]

Additional Effectiveness Analyses:

- [REDACTED]
 - [REDACTED]
 - [REDACTED]
- [REDACTED]
- [REDACTED]
- [REDACTED]
- [REDACTED]
- [REDACTED]

Study Procedure:

Subjects will be considered enrolled in the study once the patient has signed and dated the Informed Consent or DRF and the Pipeline™ Flex Embolization Device with Shield Technology™ is advanced into the micro catheter inside the patient. Per each site’s standard of care procedure, at screening, each patient can undergo a neurologic examination and assessment using the mRS and NIHSS, blood draw for hematocrit, platelet count, platelet function testing, serum creatinine, and a pregnancy test (if applicable). Pertinent medications taken by the study participant starting on the day of study procedure were collected while for platelet reactivity start date can also be > 30 days before procedure (in case patient was already under antiplatelet, including anticoagulants and antiplatelet therapy). Subjects will be assessed and documented at baseline. Patient eligibility assessment is to be performed based on data available to the investigator at the time of screening. Patient will be considered a screen failure if:

- The patient signs the informed consent or DRF but fails to meet study inclusion/exclusion criteria during the screening and baseline phase.
- The patient signs the informed consent or DRF, meets the study inclusion/exclusion criteria but an attempt to implant the Pipeline™ Flex Embolization Device with Shield Technology™ is not performed.

The investigator will assess device occlusion, device placement and overall status of the aneurysm. At the investigator’s discretion, the target IA may be retreated at any time during the study. In such situations, the date of the initial procedure (and not the date of the retreatment) will be considered Day 0.

If the target IA undergoes an attempted deployment with the Pipeline™ device with Shield Technology™ but is not implanted or receives an alternate treatment (e.g., coils), the patient is considered an implant failure and will be followed up until hospital discharge. However, if the target IA does not undergo an attempted deployment with the Pipeline™ device with Shield Technology™ and is not treated or receives an alternate treatment (e.g., coils) during the initial procedure, the patient is considered a screen failure and no further follow up is required.

The patient will be tested at the discretion of the site per standard of care procedures for antiplatelet response and the appropriate dose of antiplatelet agents will be given after the Pipeline™ device with Shield Technology™ placement procedure. Medications could be continued as medically indicated.

Estimated Duration of Patient Participation

Up to 200 subjects will be enrolled over a period of approximately 24 months. The study is intended to have 200 subjects undergo attempted deployment of the Pipeline™ device with Shield Technology™. Each study patient will be followed for 1 year after the primary study procedure. Study participation includes consent, initial screening and baseline, treatment using the Pipeline™ device with Shield Technology™, discharge exam and follow-up visits at approximately 30, 90, 180 days, and 1 year. The total study duration is expected to be approximately 3 years.

Schedule of Assessments

	Baseline	Procedure	Discharge	1 Month	3 Months	6 Months	1 Year	Unscheduled
Schedule		Day 0		±14 days	±30 days	±6 weeks	±8 weeks	
Eligibility	X							
Demographics	X							
Aneurysm Symptoms	X	O	O	O	O	O	O	OR
Medical History		X						
Study Procedure		X						
Procedure Imaging		XR						
Ancillary Devices		X						
Study Device		XR						
Discharge			X					
Follow Up				X	X	X	X	XR
Follow-Up Imaging				OR	OR	OR	OR	OR
NIHSS	O	X		O	O	O	O	OR
mRS	O	X		O	O	O	O	OR
Exit			X					

Retreatment Study Procedure				OR	OR	OR	OR	OR
Labs	OR	OR	O	O	O	O	O	OR
Device Specific Event		OR	OR	OR	OR	OR	OR	OR
Adverse Event Assessment		OR	OR	OR	OR	OR	OR	OR

Key: Required=X Optional=O Repeatable=R

ANALYSIS POPULATIONS

The following populations will be considered for the analysis of data for this study:

Intent to Treat (ITT)

The Intention to Treat (ITT) population includes all consented subjects in whom deployment of the Pipeline™ device with Shield Technology™ was attempted.

Full Analysis Set (FAS)

The Full Analysis Set (FAS) population is a subset of the ITT population including only those subjects in whom the Pipeline™ device with Shield Technology™ was implanted.

Internal Carotid Artery (ICA) Population

The Intra-Cranial Artery Population (ICA) is a subset of the ITT population including only those subjects in whom the Pipeline™ device with Shield Technology™ was implanted in the ICA (segments C2-C7).

Non-ICA Population

The non-ICA is a subset of the ITT population including only those subjects in whom the Pipeline™ device with Shield Technology™ was implanted in the arterial vessels other than those specified in the ICA population.

6. Determination of Sample Size

No formal estimates were prepared for examining the individual variables. However, the incidence of certain events will be examined relative to the thresholds used in research treating a similar population. Device outcomes variables recorded on a dichotomous scale will be summarized using a 2-sided 95% Clopper-Pearson exact binomial confidence interval. The upper and lower bounds of the confidence interval will be examined relative to results in the peer-reviewed literature and studies using the

Pipeline device without the Shield Technology™. Specifically, the incidence at 1 year post-procedure of a major stroke in the territory supplied by the treated artery or neurological death will be examined relative to an a priori threshold of 15%. The incidence at 1 year post-procedure of aneurysm occlusion without significant parent artery stenosis will be examined relative to an a priori threshold of 50%.

7. Statistical Methods

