1.2.3 Clinical Study Experience

The clinical benefits achieved with the use of use of Pipeline™ Embolization Device have been consistently demonstrated in multiple clinical trials.²⁶⁻³⁶ Pipeline™ Embolization Device demonstrates high efficacy and a good safety profile in treating aneurysms of diverse morphology, ranging from small to more complex and difficult to treat aneurysms (e.g. large aneurysms, wide-

neck aneurysms, or aneurysms with complex morphology).^{27,30,37,39-41} Clinical outcomes from 5 key studies sponsored by Medtronic/Covidien have been summarized below:

Pipeline for Intracranial treatment of Aneurysms (PITA)

The PITA study was the first prospective multicenter trial of a flow-diverting construct for the treatment of complex large and giant IAs.²⁷ Thirty-one subjects with wide-necked (>4 mm) and unfavorable dome/neck ratios (<1.5 mm) and subjects with an IA that had failed previous endovascular treatment were included. Of the 31 aneurysms, 65% were small (<10 mm) and the remaining 35% were large and giant in size. In total, 46 of 47 Pipeline™ device braids were placed successfully (97.9%). In 30 out of 31 subjects, the entire neck of the targeted intracranial aneurysm was covered by the Pipeline™ device braid. Complete aneurysm occlusion was observed in 93.3% (28/30) subjects at 180 days. Two subjects experienced a major periprocedural stroke and no deaths occurred.

Pipeline™ Embolization Device for Uncoilable or Failed Aneurysms (PUFs)

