4.3 Study Population

The study population will consist of subjects who have an intracranial aneurysm and are enrolled in the study. The treated aneurysm may be ruptured (with a Hunt and Hess grade of ≤ 3) provided that the Pipeline™ Flex Embolization Device with Shield Technology™ is used according to its Instructions for Use and its intended use during the treatment regimen.

For subjects with more than one aneurysm requiring treatment, the following guidance is to be followed for subjects to be enrolled in the study.

- If more than one aneurysm can be covered by a single Pipeline device or two overlapped devices, the multiple aneurysms treated by that device(s) may all be included in the study. A maximum of two overlapped devices in consecutive arterial segments will be permitted. The largest aneurysm meeting criteria will be designated the target aneurysm. For equal sized aneurysms, the Core Lab will designate the target aneurysm.
- If the subject has more than one aneurysm and all aneurysms requiring treatment cannot be covered by a single Pipeline device or two overlapped devices, the non-target aneurysms should be treated first. After waiting at least 30 days per exclusion criterion #1 below, the subject may return for Pipeline treatment of the target aneurysm.

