4.3.3 Point of Enrollment

Given that the prospective study population consists of patients who are already selected for flow diversion therapy and that the screening assessments consist of standard patient diagnostics for this therapy, subjects are considered enrolled in the study once the subject has signed and dated the Informed Consent or DRF and the Pipeline™ Flex Embolization Device with Shield Technology™ is advanced into the micro catheter inside the subject.

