5.6 Screen Failure

Subject will be considered a screen failure if:

- The subject signs the informed consent or DRF but fails to meet study inclusion/exclusion criteria during the screening and baseline phase.
- The subject signs the informed consent or DRF, meets the study inclusion/exclusion criteria but an attempt to implant the Pipeline™ Flex Embolization Device with Shield Technology™ is not performed.

Subjects that undergo consent but are screen failures will be exited from the study and will not be required to undergo any additional follow-up. Only the reason for subject screen failure will be recorded.

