6 ADVERSE EVENTS

The following Adverse events will be collected during the course of the study on the eCRFs.

- All Adverse Events (AE) with an underlying neurological cause (Neurological Adverse Events)
- All Device Related Adverse Effects
- All Procedure Related Adverse Events
- All Bleeding Events
- All Serious Adverse Events (SAEs)

Adverse event status will be evaluated throughout the study. These will include events occurring from the point of enrollment until a subject exits the study. If the subject is enrolled and the study procedure is attempted, but the Pipeline™ Flex Embolization Device with Shield Technology™ is not implanted for any reason, subjects will be followed to discharge and relevant safety events will be collected. Investigators must obtain all information available to determine the causality and outcome of the AE and to assess whether it meets the criteria for classification as a serious and/or

unexpected event requiring notification to the Sponsor, and, where applicable, regulatory agency and IRB/EC, within the specified reporting timeframe. AEs will be categorized using the definitions in **Section 6.1**.

All study AEs, as well as the treatment and follow-up required, should be documented in the subject's medical records and in the eCRF. All study SAEs that occur during the 1 year follow-up period will be followed by the investigator until resolution or until 30 days after the occurrence of that event. A list of potential anticipated adverse events is provided in **Section 10.2**.

Bleeding events will be captured as Adverse Events by the sites and will be graded according to the GUSTO⁴⁴ bleeding criteria as seen in

Table 6-1 by the Clinical Events Committee.

Table 6-1. GUSTO Bleeding Criteria

GUSTO Bleeding Category	Definition
Severe or Life-Threatening	Intracerebral hemorrhage Substantial hemodynamic compromise requiring treatment
Moderate	Requiring blood transfusion but not resulting in hemodynamic compromise
Mild	Bleeding that does not meet the above criteria

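### The SAP drops from ITT an enrolled subject whose device never reached the target; this raises the deployment success rate if the rate is per device advanced, and the follow-up rules for that subject conflict

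*SAP*

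**What the plan says.** **Enrolment.** Under protocol 4.3.3, a subject who has signed consent or the data release form is enrolled when the device "is advanced into the micro catheter inside the subject". SAP section 3 uses the same point: "is advanced into the micro catheter inside the patient".

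**Analysis population.** The SAP's ITT definition in section 2 requires attempted deployment. It considers the device that does not reach the target and that the operator does not try to deploy, and rules that "in the rare event that happens, that patient will not be considered part of the ITT population". SAP section 5 (Analysis Populations) and SAP 7.1.3 also require attempted deployment. Protocol 9.3 asks instead for an attempt to implant and does not mention this case.

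**Endpoint.** The only secondary effectiveness endpoint is the device deployment success rate at the target site (SAP section 5 and 7.9). The unit is the device (SAP 7.2), ITT is the primary population (SAP 7.1.3 and 7.9), and the deployment table is for ITT (SAP 7.7). Success is a binary case report form item (SAP 7.7).

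**Status and follow-up.** SAP section 5 (Study Procedure) classes a subject without attempted deployment as a screen failure who needs no further follow-up. Protocol 5.6 makes a consented, eligible subject with no attempt to implant a screen failure, and adds: "Only the reason for subject screen failure will be recorded". Protocol section 6 collects events from the point of enrolment. It also says: "If the subject is enrolled and the study procedure is attempted, but the Pipeline™ Flex Embolization Device with Shield Technology™ is not implanted", whatever the reason, "subjects will be followed to discharge and relevant safety events will be collected".

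**The concern.** The exclusion applies after enrolment and depends on how the device performed. A device that was advanced and could not be brought to the target looks like a failure to deploy at the target site. Under the SAP, its subject leaves the population in which that rate is reported.

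The rate has no success threshold, but it will be compared. SAP section 6 says that interval bounds for dichotomous device outcomes will be examined against the literature and against studies of the device without Shield. SAP section 3 mentions use in a US indication evaluation. A denominator defined differently from the comparator's would distort such a comparison.

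Safety reporting is also at stake. The same enrolled subject is either followed to discharge or exited with only a reason recorded, depending on the passage applied. A Day 0 event in that subject might not be collected, or might be missing from the adverse event summaries, which SAP 7.10 plans for the ITT and ICA populations.

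**Working it through.** The documents give no expected value or sample size calculation for deployment success, so there is no planned figure to reproduce.

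**Inputs**
- Maximum enrolment: 200 subjects (protocol 4.2, SAP section 3).
- Devices per subject: protocol 1.2.3 reports 47 devices in 31 subjects in an earlier study of the device without Shield, 47/31 = 1.52. I use N = 200 devices (1.0 per subject) and N = 300 (1.5 per subject).
- Other deployment failures: the same study placed 46 of 47 devices, so 1/47 = 2.1% were not placed. I assume about 2%, that is f = 4 of 200 or f = 6 of 300. The protocol does not say whether the one unplaced device reached the target.
- Excluded subjects, k: not in the documents. Values of 1, 2 and 4 are assumptions, with one device each.
- Intervals: two-sided 95% Clopper-Pearson (SAP section 6), treating devices as independent.

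**Direction.** An excluded subject contributes no success and at least one device. With x successes among n devices in ITT, the rate is x/n; with the k devices restored as failures it is x/(n + k). The difference is

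x/n − x/(n + k) = (x/n) × k/(n + k),

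which is never negative, and is positive when x and k are both at least 1.

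**Size.** Here n = N − k and x = N − k − f.

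| N | k | f | ITT rate (95% CI) | All-enrolled rate (95% CI) | Difference (points) |
|---|---|---|---|---|---|
| 200 | 1 | 4 | 195/199 = 97.99% (94.93–99.45) | 195/200 = 97.50% (94.26–99.18) | 0.49 |
| 200 | 2 | 4 | 194/198 = 97.98% (94.91–99.45) | 194/200 = 97.00% (93.58–98.89) | 0.98 |
| 200 | 4 | 4 | 192/196 = 97.96% (94.86–99.44) | 192/200 = 96.00% (92.27–98.26) | 1.96 |
| 300 | 1 | 6 | 293/299 = 97.99% (95.68–99.26) | 293/300 = 97.67% (95.25–99.06) | 0.33 |
| 300 | 2 | 6 | 292/298 = 97.99% (95.67–99.26) | 292/300 = 97.33% (94.81–98.84) | 0.65 |
| 300 | 4 | 6 | 290/296 = 97.97% (95.64–99.25) | 290/300 = 96.67% (93.96–98.39) | 1.31 |

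The ITT rate stays near 98% whatever k is, so the rate itself does not show the exclusions. With no other failures and k = 1 at 200 devices, ITT gives 199/199 = 100% against 199/200 = 99.5%.

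**Status, passage against passage.** Take an enrolled subject whose device was advanced, did not reach the target and was not deployed.
- SAP section 2: not in ITT.
- SAP section 5 (Study Procedure): screen failure, no further follow-up.
- Protocol section 6: enrolled, procedure attempted, not implanted, therefore followed to discharge with safety events collected.
- Protocol 5.6 and 9.3: the answer depends on whether advancing the device counts as an attempt to implant, which neither section says.

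The SAP and protocol section 6 cannot both be followed for this subject.

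**The case against.** The strongest reply is that the denominator may be the intended one. SAP section 5 aims for 200 subjects with attempted deployment, and SAP 7.1.3 builds ITT on the attempt. If the endpoint is success per attempted deployment, there is no bias. This stands as a possible reading, so a reader should not infer that the reported rate is biased under any interpretation. The documents do not settle the matter: the endpoint names the target site, and no visible text says that the rate is conditional on an attempt.

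The categories of the deployment table in SAP 7.7 are blacked out and may contain a definition. It would therefore be wrong to say that the plan has none.

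The exclusion is also openly stated and partly recoverable. SAP 7.4 tabulates screen and implant failures by reason, protocol 9.6 promises all available data from enrolled subjects, SAP 7.10 does not limit adverse event reporting to ITT, and each patient has an adverse event profile. These soften the point, and a reader could rebuild an approximate all-enrolled rate. The plan does not include one.

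Finally, protocol 4.3.3, 5.6, 6 and 9.3 agree with each other if advancing the device counts as an attempt to implant. That is fair, and it narrows the clear clash to SAP sections 2 and 5 against protocol section 6.

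**Conclusion.** The point holds conditionally. The SAP removes an already enrolled subject from ITT because the device did not reach the target. On a per-device-advanced reading of the secondary endpoint, the rate can then only be overstated, by about 0.5 point per excluded device at 200 devices and 0.33 point at 300. This assumes one device per excluded subject and a success rate near 98%. The number excluded cannot be derived from the documents, and the SAP expects it to be rare, so the likely effect is small and the intervals overlap almost entirely. The exclusion works at subject level: a device that fails to reach the target stays in the rate if deployment was attempted with another device in the same subject.

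A reader might infer that a study conclusion is at risk. The documents do not support that. SAP section 6 sets thresholds only for the two primary endpoints, and protocol 9.2 proposes no formal success criteria. The conflict over the status and follow-up of this subject stands on either reading of the endpoint, however rare the event.

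**What to change.** 1. Report deployment success by device for all enrolled subjects, using the enrolment point in protocol 4.3.3. Count a device that was advanced but did not reach the target or was not deployed as a failure, and state this in the SAP. Keep the attempt-based ITT rate as a second presentation, labelled as such.
2. Report Day 0 adverse events for all enrolled subjects as far as they were collected, and state where they were not.
3. Reconcile SAP sections 2 and 5 with protocol section 6 on the status and follow-up of this subject. Clarify in protocol 5.6 and 9.3 whether advancing the device counts as an attempt to implant.
4. As a minor note, label implantation of the study device in the ICA table as 100% by construction at subject level, because ICA membership requires implantation. The ICA and non-ICA sets can stay as defined.

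The cost is one extra table, wording changes and a slightly less favourable rate. Protocol changes need ethics approval where applicable (protocol 13.1). The SAP already describes some data collection in the past tense. Where only a screen-failure reason was recorded, procedural safety data may not be recoverable, and the report should say so.
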